Appendix B: MONITORING PLAN

Scope of the plan

The monitoring plan has the goal to verify that the conduct of the study complies with the most updated version of the Research Protocol, and in compliance with the regulation of the Institutional Review Board, the Food and Drug Administration, and the guidance of dedicated Data and Safety Monitoring Board, and the National Institute of Health.

Responsible parties

Virginia Commonwealth University, research site: [name]

Washington Hospital Center, research site: [name]

Virginia Cardiovascular Specialist, research site: [name]

Virginia Commonwealth University, investigational pharmacy: [name],

RPh

Coordinating Center Principal Investigator(s): [name]; [name],

PharmD

FDA IND Principal Investigator: [name], PhD

NIH Principal Investigator(s): [name], PhD; [name],

PharmD

The principal investigator (PI) at each local site, as indicated in the submission to the Institutional Review Board, is directly responsible for the conduct, oversight, and monitoring of study procedures at each site.

The local PI will supervise all study procedures, including the informed consent process, enrollment, withdrawal, and all decisions regarding study drug treatment.

The local PI will also be responsible for ensuring the accuracy of the data collected through verification with original source data.

Only de-identified data will be collected for the research record. However, the local PI will be able to obtain the original source documents if requested by a monitoring or inspecting

agency by linking the subject number with the identity of the subject, and retrieving the source document using document date, time and author, from the electronic medical record (or the existing paper record, if applicable).

All the shipments and handling of the investigational drug will be performed under the direct supervision of the Investigational Pharmacy Director at the Virginia Commonwealth University, who will be responsible for documentation of received and dispensed drug, storage, handling and preparation for patient use. The randomization log is also kept in the Investigational Pharmacy and is used for patient allocation. The randomization code will be kept secret and released only to the PI upon written request. The local PI may request breaking the randomization code if deemed necessary for patient care, see Protocol for details.

The handling and dispensing of the investigational drug at each individual site will occur under the direct supervision of the local PI, also listed as FDA IND investigator on the 1572 Form.

Communication between the study investigators and the FDA will occur through the IND principal investigator, or, if not available, through one of the IND investigators. Investigators other than those listed on the 1572 Form will have no role in handling or dispensing the investigational drug, nor will have any role in decision making in this regard.

The local investigators and coordinators will respond directly to the local PI. The coordinating center PI at the Virginia Commonwealth University will be responsible for oversight of individual local PIs.

The local PI is responsible for communication with the coordinating center. Such communication will occur either by phone (direct and protected line [[contact]]), by secure [contact]) or by secure email ([contact] OR [contact]).

The local PI is responsible for completing the data collection sheet and also for providing a de-identified copy of the source documents (while maintaining ability to access and provide de-identified data if necessary) in a timely manner.

The local PI is responsible for complying with the regulations set for reporting of adverse events or non-compliance with the research procedure to the local Institutional Review Board and at the same time to Coordinating Center PI.

The Coordinating Center PI will be responsible of informing all local PIs, and also for complying with the regulations set for reporting of adverse events to the Data and Safety Monitoring Board, the FDA, and the NIH.

Appendix C: Case Report Forms

- Screening and Enrollment form (1 page)
- Enrollment check list (1 page)
- Enrollment Log (1 page)
- Individual Patient Cover Sheets (3 pages)
- Individual Visit Assessment Form (4 pages)
- Adverse Event reporting form (1 page)

VCU-ART3	Screenin	g and enrol	lment f	orm	
Subject number: VCU-ART	3	Initials	Date		
INCLUSION CRITERIA: (A	ll 3 criteria ne	eed to be met)			
Presentation to the hospit defined as chest pain (or elevation (>1 mm) in 2 or r	equivalent) wi	th an onset withir	12 hours	and ECG evic	lence of ST segment
Coronary angiogram for and enrollment in the stu					
Age>21 (NIH standard)					
EXCLUSION CRITERIA (ch		plicable → patien	t excluded	a/) :	
 Inability to give informed 					
 Pregnancy or breastfeedi 	•				
Preexisting congestive here				York Heart As	ssociation III-IV)
Preexisting severe left ve	•	•	20%)		
Preexisting severe valvula		ase			
Active infections (acute of the control of the	•				4 P 20 14 12 1
 Recent (<14 days) or acti dose corticosteroids [>1 not including NSAIDs or 	mg/kg of pre	dnisone equival	ent], TNF	-alpha blocke	_
o Chronic auto-immune or a					to rheumatoid
arthritis, systemic lupus					
 Known active malignancy 	-	•	is in the p	ast 10 years	
o Anticipated need for card		, ,		,	
 Neutropenia (absolute ne patients]) 		t<1,800/mm ³ [or	<1,000/n	nm ³ in Africar	n-American
 Severe impairment in ren Recent or planned use of 	vaccination	with live attenua			
desensitization during co	irrent admiss	sion			
Allergy to rubber or latex	-1 6 F	antalata a a D			
Allergy to products derive	d from Esche	erichia coli			
Inclusion and exclusion crite	eria verified b	у	on	(date	e)
Patient given a copy of t answered.	he informed	consent and suf	ficient time	e to read and	have questions,
The original signed copy additional copy is placed			ned copy i	is given to the	e patient, and an
The consenting process is o	completed by			on	_(date)

Version Nov-20-2015

VCU-ART3

Enrollment Check List

VCU-	ART3 Subject Number InitialsSiteDate
	Check Inclusion/Exclusion criteria and sign the "Screening and Enrollment Form"
	Review Informed Consent Form with Patient and complete all signatures (patient
	and person who conducted informed consent discussion)
	Give patient a copy of the signed consent form and Research Team contact card
	Give a copy of the consent to secretary to be placed in the patient's chart
	Order Investigational Drug on Cerner
	Call Investigational Pharmacy (or ICU Pharmacy if overtime)
	Review the "Nurse Protocol" with the Nurse
	Fill VCU Lab Sheet Form completing parts highlighted in yellow
	Have nurse to collect blood sample and apply Label from "Labs Sheet Form"
	Send sample to send to VCU Central Lab (tube station #160)
	Witness nurse administer investigational drug
	Complete Data Collection Form (Initial Assessment: STEMI presentation, etc)
	Complete Vital Signs Form
Enroll	ment Check List verified by (Initials) on (date)

VCU-ART3 - ENROLLMENT LOG -- Site _____

	(initials	3, 2 4.00,
1		
2		
3		
4		
5		
6		
7		
8		
9		
10		
11		
12		
13		
14		
15		
16		
17		
18		
19		
20		
21		
22		
23		
24		
25		

ENROLLED (Initials/Date) **EXCLUDED** (reason oly)

	LD (reason dry)
E1	
E2	
E3	
E4	
E5	
E6	
E7	
E8	
E9	
E10	
E11	
E12	
E13	
E14	
E15	
E16	
E17	
E18	
E19	
E20	
E21	
E22	
E23	
E24	
E25	

HM20000024 - Interleukin-1 blockade in acute myocardial infarction Participant Study ID: Hospital Admission Date: __/_/ Hospital Discharged Date: __/_/ Length of Stay in the Hospital: Questions: Was the patient in the ICU? NO / YES Drug Dispensed to Participant If YES, how long? Date: / / # of syringes dispensed: Date for 14-day follow-up: / / - Was the patient re-admitted between baseline and 14-day FU? NO / YES Drug Returned by Participant at 14-day FU Was the patient re-admitted between 14-day FU and 12-Date: / / week FU? NO / YES # of syringes returned: - Was the patient re-admitted between 12-week FU and 24-week FU? NO / YES Was the patient re-admitted between 24-week FU and 52-week FU? NO / YES If Re-Consented: Eligibility Confirmed on __/_/___ Date ICF signed: __/_/___ Signed/Performed by: _____ Withdrew Consent: Date: __/__/__ Reason? Notes: Informed Consent: Version / / IRB approval _ / _ / _ _ ; signed on _ / _ / _ Notes: Randomization: __/__/ Study Time Point Study Procedure Completed Notes Note in CIS re: Clinical Trial/ICF Process Blood Draw (baseline - HDL or VCU) Concomitant Rx Baseline (Day 1) Baseline History __/__/___ Drug Ordered Drug Dose #1 administered Echocardiogram (ordered) Drug Dose #2 administered AE review Drug Dose #1 administered Day 2 (24 hrs) Drug Dose #2 administered _ / _ / Other: AE review Drug Dose #1 administered Day 3 (48 hrs) Drug Dose #2 administered __/__/ Other:

	HM20000024 – Interleukin-1 blockade in acute myocardial infarction					
	72 hrs Labs (HDL)					
Day 4 (72 hrs)	AE review					
/ /	Drug Dose #1 administered					
	Drug Dose #2 administered					
	Other:					
	AE review					
Day 5	Drug Dose #1 administered					
//	Drug Dose #2 administered					
	Other:					
	AE review					
Day 6	Drug Dose #1 administered					
//	Drug Dose #2 administered					
	Other:					
	AE review					
Day 7	Drug Dose #1 administered					
	Drug Dose #2 administered					
	Other:					
	AE review					
Day 8	Drug Dose #1 administered					
	Drug Dose #2 administered					
	Other:					
	AE review					
Day 9	Drug Dose #1 administered					
	Drug Dose #2 administered					
	Other:					
	AE review					
Day 10	Drug Dose #1 administered					
	Drug Dose #2 administered					
	Other:					
	AE review					
Day 11	Drug Dose #1 administered					
	Drug Dose #2 administered					
	Other:					
	AE review					
Day 12	Drug Dose #1 administered					
	Drug Dose #2 administered					
	Other:					
	AE review					
Day 13	Drug Dose #1 administered					
/ /	Drug Dose #2 administered					
	Other:		1			
	Blood Draw (14-day HDL)					
	AE review		1			
Day 14	Investigational Drug Reconciliation		1			
//_	Concomitant Rx		1			
			1			
	Other:					

HM20000024 - Interleukin-1 blockade in acute myocardial infarction Blood Draw (12-week HDL) Concomitant Rx 12-week FU __/__/___ AE review Other: Blood Draw (24-week HDL) Concomitant Rx 24-week FU AE review __/__/___ 12-month Echocardiogram ordered Other: Blood Draw (52-week HDL) Concomitant Rx 52-week FU AE review __/__/___ 1-year Echocardiogram Other: Additional Notes: SAEs Reported?Deviations?

	VCU-ART3 Subject # Init	ials	Clinical Site:	vcu / vcs / whc		
	Initial Assessment: STEMI present	ation				
Date	e, time of symptom onset	, ED a	rival,	PCI time		
ECG	G - ST segment elevation (circle all t	hat apply): \	′1 V2 V3 V4 V5	V6 I II III aVF aVL		
[]h	Clinical conditions: (check all that apply) [] hypotension/shock; [] pulmonary edema; [] ventricular arrhythmias [] persistent pain; [] altered mental status					
[]t	cedural data: check all that apply) thrombectomy; [] stent implantati pivalirudin; [] abciximab/eptifibatide; [] as					
[] F [] C	t Medical History: (check all that ap Prior MI; [] Prior PCI; [] Prior CABo Diabetes; [] Hyperlipidemia; [] Cu Chronic Kidney Disease; [] Chronic tes	G; [] Heart rrent Tobac	co user; [] Pe	ripheral Vasc Disease	on	
[] ([] I [] N Bod Bloc	JDY ITEMS: (check all completed) Consenting; [] Initial Labs (local/ce Investigational drug first dose admi Medication Reconciliation; [] Echo dy weight:kg/lb He od Pressure:/ mmHg H 72 h Labs (±12 hours) (local/central	nistered on cardiogram eight:n R:mir	// ordered (poss n/ft n	at:AM/PM ibly <24 hrs) BMI:kg/m ²		
[] h [] v [] a [] r Dura	spital outcomes (check all that appl hypotension/shock, check [] if requipulmonary edema, check [] if requipulmonary edema, check [] if requipulmonary enal failure, check [] if requipulmonary en	uiring inotro uiring mecha f sustained, iring renal re PCI; [] stage	inical ventilati requiring card eplacement th	on lioversion		
[] [[] F [] C	CHARGE PLANNING: (check all com Dispensing of investigational drug (Patient education on drug handling Outpatient Hospital Follow up (11-1 Discussed with patient how to cont	syringe , storage, an L7 days) sche	d self-adminis eduled on	stration (by) (location))	

	VCU-ART3 Subject # Initials Clinical Site: VCU / VCS / WHC						
	Follow up visit #1: 14 day (11-17 days)						
Date of STEMI, Date of F/U visit							
[] [] []	ical conditions: (check all that apply) recurrent angina/myocardial infarction, check [] if leading to re-hospitalization heart failure symptoms, NYHA class (I→IV), check [] if re-hospitalization re-hospitalization for other cause (complete dedicated sheet) death, check [] if presumed cardiac death, check [] if sudden death res						
[]	t Medical History: (changes vs prior – new diagnoses); []; []; []; []						
[] [] [] Boo	Assessment of compliance with investigational drug performed by used syringes; returned syringes) Send-out Labs (HDL); [] Medication reconciliation; Scheduling F/U visit for, location ly weight:kg/lb						
	Follow up visit # 2: 3 months (10-14 weeks)						
Dat	e of STEMI, Date of F/U visit						
[] [] []	recurrent angina/myocardial infarction, check [] if leading to re-hospitalization heart failure symptoms, NYHA class (I→IV), check [] if re-hospitalization re-hospitalization for other cause (complete dedicated sheet) death, check [] if presumed cardiac death, check [] if sudden death res						
[]	t Medical History: (changes vs prior – new diagnoses); []; []; []; es;						
[] [] Boo	IDY ITEMS: (check all completed) Send-out Labs (HDL); [] Medication reconciliation; Scheduling F/U visit for, location ly weight:kg/lb						

,	VCU-ART3 Subject #	Initials	Clinical Site:	VCU / VCS	S / WHC
	Follow up	visit #3: 6 months	(22-26 weeks)		
Date	of STEMI, Date of	F/U visit	_		
[]re []he []re []de	cal conditions: (check al current angina/myocard eart failure symptoms,hospitalization for other eath, check [] if presums	dial infarction, chec NYHA class (I- er cause (complete o	→IV), check [] i dedicated sheet	f re-hospit	
[]_	Medical History: (chang ;[]s s	;[]	;[]		 
[] Se [] Re [] Fo Body	or ITEMS: (check all comend-out Labs (HDL); [] Nepeat echocardiogram to llow up visit forkg/ld Pressure:/ n	Medication reconcili to be scheduled for 2, location b	12 month visit _m/ft	вмі:	kg/m²
	Follow up	visit #4: 12 months	(11-13 months))	
Date	of STEMI, Date of	F/U visit	_		
[]re []he []re	cal conditions: (check al current angina/myocard eart failure symptoms, _ -hospitalization for othe eath, check [] if presums	dial infarction, chec NYHA class (I- er cause (complete	→IV), check [] i dedicated sheet	f re-hospit	
[]_	Medical History: (chang ; []s ss	[];			
[] Se [] Re [] So	oy ITEMS: (check all comend-out Labs (HDL); [] Nepeat echocardiogram; theduling F/U visit with	Medication reconcili			
	weight:kg/l			BMI:	kg/m²
טטטום	d Pressure:/ n	шпав ш к	11111		version 040620

	VCU-ART3 Subject # Initials Clinical Site: VCU / VCS / WHC					
	Follow up visit: Extra-visit					
D	ate of STEMI, Date of F/U visit					
]]]	Clinical conditions: (check all that apply) [] recurrent angina/myocardial infarction, check [] if leading to re-hospitalization [] heart failure symptoms, NYHA class (I→IV), check [] if re-hospitalization [] re-hospitalization for other cause (complete dedicated sheet) [] death, check [] if presumed cardiac death, check [] if sudden death Notes					
[ast Medical History: (changes vs prior – new diagnoses)]; []; []; [];					
s · [[B	TUDY ITEMS: (check all completed)] Send-out Labs (HDL); [] Medication reconciliation;] Repeat echocardiogram to be scheduled for 12 month visit] Follow up visit for, location ody weight:kg/lb					

version 04062015

VCU-ART3 study

Version April 6, 2015

Initials

VCU-ART3 Study EVENT FORM

VCU-ART3 Subject

• -	
Hospitalization, date	Death, date
 □ Acute Decompensated Heart Failure as primary diagnosis (see Protocol) □ Acute Coronary Syndrome as primary diagnosis □ Arrhythmia as primary diagnosis □ Acute Renal Failure □ Acute Respiratory Failure (not due to heart failure) □ Sepsis, or Severe Infection □ TIA/Stroke □ Other (Specify) 	 □ Out of hospital and sudden □ In-hospital, associated with ventricular arrhythmia not secondary to other cardiac disease □ In-hospital, associated with acute cardiac issue □ In-hospital, associated with acute non cardiac issue (Specify) □ Other (Specify) □ Unknown
Other events date	
(not leading to hospitalization)	ADVERSE EVENT: YES ☐ NO ☐
 □ Injection site reaction □ Rash □ Fever □ Infection (requiring antibiotic tx □) □ Nausea/Vomiting/Diarrhea □ Others: (Specify) 	ANTICIPATED □, NOT ANTICIPATED □ SEVERITY: MILD □; MODERATE □; SERIOUS □
Interruption of Treatment,	RELATED TO RESEARCH:
date ☐ Mandated by protocol ☐ Decision made by patient	UNRELATED □; POSSIBLY □; PROBABLY □; DEFINITELY □
	and RELATED TO RESEARCH → E PRINCIPAL INVESTIGATOR(s)
Completed By, Name Signature	Date
Attach de-identified Notes from chart or not	es (check if not available)
Principal Investigator(s) Signature	Date
Prompt report to the IRB/DSMB needed	completed D by on

	VCU-ART3 Ec	hocardioDoppler A	nalysis	
	Date S	ubject number:	Initials	
I I I I I I	ip as part of standard clini mages to be acquired on a neasurements. The study requires a Limite deemed necessary, then pro Measurements for research	cal care. The patient and digital format and then a digital format and then a digital format and then a digital format and ceed with full studypurposes do not need to didual center, they will be	rly as possible) and at 12 me Insurance may be billed for transferred to VCU for centr alysis – if a more complete e be performed on-line, neith performed single batch at t	: al lab exam is er need to
Ob	otain apical 4-chamber v	iew:		
	 Record 2 dimensio 	n imaging to measure	LVEDV and LVESV	
			o LVEDV / LVESV	
	 Record Color-Dopp 	ler of Mitral Inflow an	d Regurgitation	
			 Quantify regurgitation 	1
	 Record Color-Dopp 	ler of Left Ventricular	Outflow tract	
	 Record transmitra 	l Doppler flow spectra	E/ DT/ A	HR
	Record lateral wall	Mitral Annular tissue	Doppler spectra	
			E'lat/A'lat/ S'lat	
	 Record septum Mit 	ral Annular tissue Dop	pler spectra	
			E'sept/ A'sept/ S	s'sept
	 Record Tricuspida 	Annulus tissue Doppl	er spectra S'lat	
	 Record TAPSE (M-1 	node)	Excursion_	
0	btain apical 2-chamber	view:		
	• Record 2 dimensio	n imaging to measure	LVEDV and LVESV	
			o LVEDV / LVESV	
				Version Jun-16-2014

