8.3 Methods of Timing for Assessing, Recording, and Analyzing Safety Parameters

8.3.1 Adverse Events

All Adverse Effects (AEs) will be recorded on an AE form regardless of causality.

An AE is defined as any untoward medical occurrence in a patient or clinical investigation subject administered a pharmaceutical product considered to causally related to the study treatment or research conduct. An AE can therefore be any unfavorable and unintended sign (including an abnormal laboratory finding), symptom, or disease temporally associated with the use of medicinal (investigational) product. The occurrence of an AE may come to the attention of study personnel during study visits and interviews of a study recipient for medical care, or upon review by an investigator or study coordinator. An event that is considered by the investigator(s) to be expected and related to the natural history of the disease is NOT considered an AE.

All events considered AEs including local and systemic reactions not meeting the criteria for "serious adverse events" will be reported on the appropriate AE form. Information to be collected includes event description, time of onset, clinician's assessment of severity, relationship to study intervention (assessed only by those with the training and authority to make a diagnosis, which would include a physician) and time of resolution/stabilization of the event. All AEs occurring while on study must be documented appropriately regardless of relationship. All AEs will be followed to adequate resolution.

Any medical condition that is present at the time that the patient is screened should be considered as baseline and not reported as an AE. However, if it deteriorates at any time during the study, it should be recorded as an AE.

All AEs must be graded for severity and relationship to study product.

Severity of Event: All AEs will be assessed by the clinician according to the following guidelines to quantify intensity:

 Mild: events require minimal or no treatment and do not interfere with the patient's daily activities.

- Moderate: events result in a low level of inconvenience or concern with the therapeutic measures. Moderate events may cause some interference with functioning and may require systemic drug therapy or other treatment.
- Severe: events interrupt a patient's usual daily activity and may require systemic drug therapy or other treatment. Severe events are usually incapacitating.

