- Life threatening: any adverse drug experience that places the patient or subject, in the view of the investigator, at immediate risk of death from the reaction as it occurred (i.e. does not include a reaction that might have caused death had it occurred in a more severe form).

Changes in the severity of an AE will be documented to allow an assessment of the duration of the event at each level of intensity to be performed. Adverse events characterized as intermittent require documentation of onset and duration of each episode.

Relationship to the intervention: All suspected AEs must have their relationship to study intervention assessed using the terms: associated or not associated. In a clinical trial, the study intervention must always be a suspect. To help assess, the following guidelines are used to assess causality:

- Definitely related: The event is temporally related to the administration of the study intervention and, in the opinion of the investigator, no other etiology explains the event.
- Probably related: The event is temporally related to the administration of the study intervention and represents, in the opinion of the investigator, the most plausible explanation of the event.
- Possibly related: The event is temporally related to the administration of the study intervention but, in the opinion of the investigator, it does not represent the most likely explanation of the event.
- Definitely Unrelated: The event is temporally independent of study intervention and/or the event appears, in the opinion of the investigator, to be explained by another etiology.

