10.1 Reasons for Discontinuation of Treatment or Withdrawal from the Study

Patients may withdraw from the study at any time. The investigators can withdraw any patient at any time from the study if medically necessary. It will be extremely important to obtain complete follow-up data on each patient, except on those who withdraw consent to release such information. It will be documented whether or not each patient completed the study. If for any reason the study treatment or observations were discontinued, the reasons will be recorded and the IRB will be informed.

Reasons for discontinuation of anakinra (or placebo):

- 1) Neutropenia (ANC<1000/mm³)*;
- 2) Systemic infection (sepsis)*;
- 3) Surgery *;
- 4) Cancer;
- 5) Hypersensitivity reaction (rash, anaphylaxis);
- 6) Severe injection site reactions *;
- 7) Need for immunosuppressant therapy;
- 8) Stroke *.

^{*} treatment may be restarted after condition resolved

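### The Study Event Form offers mild, moderate and serious as severity options, so two of the four severity grades required by section 8.3.1 have no coded box

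*Combined protocol and SAP*

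**What the plan says.** Section 8.3.1 makes grading mandatory: "All AEs must be graded for severity and relationship to study product". It then defines a four-step intensity scale:

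- the first step is "Mild: events require minimal or no treatment";
- the second is "Moderate: events result in a low level of inconvenience or concern with the therapeutic measures";
- the third is severe, of which the protocol says "Severe events are usually incapacitating";
- the fourth is "Life threatening: any adverse drug experience that places the patient or subject" at immediate risk of death.

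The section also asks for changes in severity to be recorded, so that the time spent at each intensity level can be assessed.

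Section 8.3.2 defines a serious adverse event on a different basis. The event must lead to one of a list of outcomes (death, threat to life, admission or longer stay, lasting disability, or an important medical event). The investigator must also judge it unexpected or out of keeping with the course of the disease.

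The Study Event Form in Appendix C has one severity line. It opens with "SEVERITY: MILD" and its three options run: "SEVERITY: MILD □; MODERATE □; SERIOUS".

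Section 10.1 lists "Severe injection site reactions" among the reasons for discontinuing study drug.

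**The concern.** Severity describes how intense an event is. Seriousness describes what it led to or threatened, and it drives regulatory reporting. The protocol keeps the two apart: under 8.3.1, events that fall short of the serious criteria still go on the adverse event form with a severity assessment. The form puts the seriousness term on the severity scale.

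At stake is the quality of the coded safety data. Safety is a stated objective in section 5, and the trial includes a twice-daily regimen, whereas the pilot studies used 100 mg once daily. The gap also touches the drug's best-known reaction. The background section describes injection-site reactions as mostly mild with the occasional severe case, and section 10.1 attaches a consequence to the severe ones. If the word severe cannot be ticked, the grade that 10.1 relies on is not a coded item on this form.

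**Working it through.** No arithmetic applies beyond a count of categories. Setting the two scales side by side:

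| Grade in section 8.3.1 | Box on the Study Event Form |
|---|---|
| Mild | Mild |
| Moderate | Moderate |
| Severe | none |
| Life threatening | none |
| (not a grade) | Serious |

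So 4 protocol grades meet 3 boxes. Two match, 4 − 2 = 2 grades have no box, and 3 − 2 = 1 box is not a grade.

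The next question is whether any reading of the third box rescues the form.

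1. **Read as serious in the sense of 8.3.2.** A severe, non-serious event then has no correct box. It is under-graded as moderate or wrongly flagged as serious. For an event that is serious, ticking this box loses its intensity, whether that was moderate, severe or life threatening.
2. **Read as a slip for severe.** Severe events then have a box, but life-threatening events still do not, and the legible form no longer records seriousness anywhere as a yes/no item.

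Neither reading recovers both the four grades and the seriousness flag. The form does not say which is meant, so staff at different sites could apply different readings, and the pooled category would then have no single meaning.

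Injection-site reactions show where the first reading bites. The form lists them among events that did not lead to admission, so they will usually not meet 8.3.2. A severe one is therefore a typical severe, non-serious event.

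By contrast, the form's relatedness line has four levels (unrelated, possibly, probably, definitely) that correspond to the four causality categories of 8.3.1. The mismatch is confined to the severity line.

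**The case against.** The strongest reply is that other fields limit the loss.

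- **Discontinuations.** The form has an injection-site reaction box and a dated treatment-interruption field with an option for interruption required by the protocol. A reaction that triggers the 10.1 criterion can largely be identified from that combination, whichever severity box is ticked. This stands. What remains uncoded is a severe reaction not recorded as an interruption.
- **Attached notes.** De-identified notes are requested, so the grade may be recoverable. But notes are not coded data, and the form allows them to be unavailable.
- **SAE form.** Section 8.4.1 refers to a separate SAE form. It is not in the Appendix C list, but that list is not exhaustive, since the echocardiography form is also absent from it. Such a form could hold detail on serious events, but it would not supply a grade for severe events that are not serious.

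A reader might also infer stronger consequences. The documents do not support them:

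- **Distorted severity tables by arm, or a misled DSMB.** No such table is specified. The statistical analysis section does not mention adverse-event severity, and the DSMB charter leaves the content and format of its reports for the board to discuss.
- **About 16 or 17 patients affected.** Applying the pilot rate of 5 of 20 (25%) to 2 × 33 = 66 anakinra patients gives 0.25 × 66 = 16.5. That counts reactions of any grade, and mild and moderate ones have correct boxes. The rate also comes from pilots of once-daily dosing, whereas every arm here injects twice daily.
- **Life-threatening events indistinguishable from routine admissions.** The form separates hospitalisations by main diagnosis, deaths by circumstance, and events without admission. What is missing is only a coded life-threatening grade.
- **Failure of expedited reporting.** The form records anticipation, relatedness and the need for a prompt report separately, and reporting rests on sections 8.3.2 and 8.4.1. The instruction that might use the serious box is incomplete in the available text, so nothing can be concluded from it.

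**Conclusion.** The form and the protocol disagree, and following the form as printed gives wrong or incomplete severity codes for events above moderate. The size in categories is exact: two of four grades are missing, and one option belongs to a different concept. The size in events is unknown, because no rate of severe reactions is given.

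This rests on two assumptions: that the severity line shown is the one in use, and that no field outside the legible text records seriousness or the missing grades. The effect is limited to the capture and summary of safety data. The CRP primary endpoint, the sample size and the named secondary endpoints do not depend on this line. The point is worth correcting because the protocol makes grading mandatory and the correction is cheap, not because any trial conclusion has been shown to be at risk.

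**What to change.** Replace the three options on the Study Event Form with the four grades of section 8.3.1: mild, moderate, severe, life threatening. Add a separate field, *Serious (8.3.2 criteria): yes/no*, so that intensity and seriousness are each recorded for every event. This applies the protocol's existing definitions and changes no clinical rule.

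The documents do not show whether any forms have been completed. If some have, re-grade them from the attached notes, blinded to treatment allocation, and mark those without notes as not gradable rather than imputing a grade.

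The cost is a minor form revision and, if forms exist, limited re-coding. Some earlier events may remain ungraded.
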